Original Article NCT03615755

Short Duration Hyperbaric Oxygen Therapy to Improve HbA1c, Leukocyte, and Serum Creatinine in Patient with Diabetic Foot Ulcer Wagner 3-4

Author:

dr. [name]

Surgery Department, Faculty of Medicine, Udayana University, Sanglah General Hospital, Denpasar, Indonesia.

Co-Author 1:

Dr. dr. [name], Sp.B, Sp.BTKV

Thorax and Cardiovascular Surgery Division, Surgery Department, Faculty of Medicine, Udayana University, Sanglah General Hospital, Denpasar, Indonesia.

Co-Author 2:

[name]. dr. [name], Sp.PD-KGH

Nephrology and Hypertension Division, Internal Medicine Department, Faculty of Medicine, Udayana University, Sanglah General Hospital, Denpasar, Indonesia.

Correspondence:

Name : dr. [name]
[contact]
Email : [contact]
Affiliation : Surgery Department, Faculty of Medicine, Udayana University, Sanglah General Hospital, Denpasar, Indonesia.
Address : [name].

Denpasar, 10-04-2018

dr. [name]

Methods

This study uses pretest and posttest control group design, to know the role of standard therapy and combination therapy (standard therapy with adjuvant HBOT) to decrease HbA1c levels, leukocyte count, and serum creatinine levels in DFU patient Wagner 3-4. All DM patients with DFU at Sanglah General Hospital, Denpasar who meet the inclusion and exclusion criteria and willing to follow the research procedure. All patients are signing the agreement paper after getting research explanation. All patients were briefed on the study research using HBOT. If they are willing to participate in the study and use HBOT was grouped to combination therapy, if they are willing to participate in the study but do not want to use HBOT was grouped to standard therapy, but if they are not willing participate then excluded. The study was approved by Institutional Review Board of Medical Faculty of Udayana University and Sanglah General Hospital Denpasar with the ethical number 580/UN.14.2/KEP/2016.

Thirty diabetic patients with DFU Wagner 3-4 were participated in this study. All patients were taken blood test for HbA1c levels, leukocyte count, and serum creatinine levels before debridement, then grouped for standard therapy or standard therapy with 10 sessions of HBOT. One session of HBOT uses oxygen at 2.4 ATA for 90 minutes per day at multiplace hyperbaric chamber. This therapy is given five sessions in a week, so it takes two weeks. At the end of therapy, all blood tests were performed again in both groups.

The inclusion criteria were patients who had type 2 diabetes and DFU Wagner class 3 or 4, aged over 18 years, and underwent debridement with or without toe amputation. The exclusion criteria were patients who had severe organs dysfunction such as heart failure, pulmonary infection, pneumothorax, chronic obstructive pulmonary disease, and stroke.

Statistical analysis using SPSS 17.0 (SPSS Inc., Chicago, IL, USA). All variables were described before and after treatment. Analysis pretest and posttest values on both groups were used paired T-test and independent T-test. The statistical test results are significant if $p < 0.05$.

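### The aim takes in the role of standard therapy, but both groups receive it, so only uncontrolled paired tests could speak to that part of the aim

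*Protocol*

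**What the plan says.** The first paragraph of Methods in the protocol describes the design: "This study uses pretest and posttest control group design". It then states the purpose: "to know the role of standard therapy and combination therapy (standard therapy with adjuvant HBOT) to decrease HbA1c levels", followed by leukocyte count and serum creatinine. Read literally, standard therapy is something to be studied alongside the combination.

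The same paragraph assigns groups by the patient's willingness to have HBOT: "if they are willing to participate in the study but do not want to use HBOT was grouped to standard therapy". The second paragraph confirms what each group gets. After baseline sampling, patients were "then grouped for standard therapy or standard therapy with 10 sessions of HBOT". Standard therapy is common to both groups, and no group goes without it.

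On timing, "All patients were taken blood test for HbA1c levels, leukocyte count, and serum creatinine levels before debridement". Debridement, with or without toe amputation, is an inclusion criterion, so every patient has surgery between the two blood samples. The second sample is taken when therapy ends, after about two weeks.

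The analysis paragraph says: "Analysis pretest and posttest values on both groups were used paired T-test and independent T-test". Significance is set at p < 0.05. It does not say which test answers which part of the aim.

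**The concern.** A claim about what a treatment does to a marker needs a comparison in which that treatment differs. Here HBOT is the treatment that differs by plan. The independent t-test can speak to HBOT added to standard therapy, subject to the separate weakness that patients chose their own group. It cannot speak to standard therapy, because standard therapy is the same on both sides of the comparison.

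That leaves the paired test as the only planned analysis bearing on the role of standard therapy. It compares patients with themselves, from a point at which they had a Wagner 3-4 ulcer about to be debrided to a point some two weeks later. Any fall counts in full, whatever caused it. The paired test in the combination group has the same defect, and there it matters more for the question in the title: a significant before-after fall could be taken as evidence for HBOT although nothing in that test isolates HBOT.

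What is at stake is the conclusion the study may draw, not the conduct of the study. Randomising patients to HBOT would not cure the part about standard therapy, since both groups would still receive it.

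**Working it through.** The protocol contains no power or sample-size calculation, so there is no figure to reproduce. The point rests on setting the statements side by side; the arithmetic afterwards is only an illustration.

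**Aim against design and tests**

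| Part of the aim | Contrast that would answer it | In the study? | Planned test that bears on it |
|---|---|---|---|
| Role of standard therapy | With versus without standard therapy | No; both groups receive it | Paired t-test in the standard group (no comparator) |
| Role of the combination as a whole | Combination versus neither component | No | Paired t-test in the combination group (no comparator) |
| Added effect of HBOT | Standard plus HBOT versus standard alone | Yes | Independent t-test between groups |

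Only the third row has a comparison behind it, and the aim as worded does not state it.

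**What a paired test picks up**

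In either group, the expected before-after change is the sum of the effect of the assigned treatment, the natural course over about two weeks, the effect of the debridement that falls between the samples, and any regression to the mean. The paired test asks only whether the sum is zero. If debridement is counted as part of standard therapy, which the protocol does not define, it stops being a rival explanation in the standard group, but natural course and regression to the mean remain.

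**Illustration**

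Inputs:
- Total of 30 patients, from Methods.
- Significance at p < 0.05, from Methods; two-sided is assumed because sidedness is not stated.
- 15 patients in a group: an assumption (30 / 2), because group sizes are not stated and follow from patients' choices.
- Treatment effect zero, with a drift from other causes of *d* SDs of the within-patient change: an assumption, because no SD is given.

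Formula: the paired t statistic follows a noncentral t distribution with n − 1 degrees of freedom and noncentrality d × √n. The probability of significance is P(|T| > t₀.₉₇₅,ₙ₋₁).

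With n = 15, the critical value on 14 degrees of freedom is 2.145 and √15 = 3.873:

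| d | Noncentrality | P(significant) |
|---|---|---|
| 0 | 0 | 0.050 |
| 0.2 | 0.2 × 3.873 = 0.775 | 0.112 |
| 0.5 | 0.5 × 3.873 = 1.936 | 0.438 |
| 0.8 | 0.8 × 3.873 = 3.098 | 0.821 |

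Sensitivity to the unknown group size, at d = 0.5: 0.293 with n = 10 (noncentrality 1.581) and about 0.56 with n = 20 (noncentrality 2.236). More patients make a significant result from drift alone more likely, so a larger sample does not help.

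**The case against.** Four points can be made on the other side.

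1. *No sentence in the protocol says that a significant paired test will be credited to standard therapy.* This is correct. A reader might infer such a rule from the aim and the only test that could serve it, but the analysis paragraph gives two tests and a threshold and no rule of interpretation. A statistical analysis plan, if one exists, could settle how the tests are read. What stands is that the result could be read that way, and that an analysis plan cannot supply the missing comparison.

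2. *The phrase about the two therapies may simply name the two arms.* The title asks about HBOT, the design is described as having a control group, and allocation turns on HBOT alone. This reading is reasonable. It also means that a reader who concludes that half the study question is unanswerable goes too far, since that rests on one loosely worded phrase. It does not remove the need to reword: if the intended question is HBOT, the aim should say so.

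3. *The percentages are not error rates of this trial.* This is also correct. A reader might set 44% or 82% against the nominal 5% and see an inflated type I error. The paired test's null hypothesis is zero mean change, and the assumed drift makes that false, so these figures are the test's power to detect the drift. The drift sizes and the 15 per group are not in the protocol. Eligibility also sets no threshold on HbA1c, leukocytes or creatinine, so the amount of regression to the mean is unknown and may differ between the three markers.

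4. *The plan already describes the variables before and after treatment and includes an independent t-test.* True, and this is why the remedy is small. But the paired tests are listed beside the independent test at the same threshold, and nothing marks them as descriptive.

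**Conclusion.** The point holds as one about the wording of the aim and the reading of the paired tests. The aim names standard therapy as something whose role is to be learned, every patient receives it, and no planned contrast varies it. A before-after fall in either group cannot be separated from natural course, intervening surgery or regression to the mean. This follows from the text of Methods and needs no numerical assumption.

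Its size cannot be estimated from the protocol. Under an assumed 15 patients in a group and an assumed treatment-unrelated drift of 0.2, 0.5 or 0.8 SD of the change, a paired test would be significant in about 11%, 44% or 82% of studies. These figures show only that a significant paired result does not identify its cause.

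The documents do not support the stronger statement that the plan will attribute such a fall to standard therapy. The between-group comparison itself is not affected by this point; its weakness from self-selected allocation is a separate matter.

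**What to change.** Make three changes of wording in Methods:

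- Restate the aim as the added effect of HBOT on HbA1c, leukocyte count and serum creatinine when given on top of standard therapy, and drop the role of standard therapy as something the study tests.
- State that the conclusion about HBOT rests on the between-group comparison only.
- State that before-after changes in both groups are reported as description, for example as mean change, and that no conclusion about treatment effect is drawn from either group's paired test.

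The cost is a reworded aim and a sentence or two in the analysis paragraph, with no new patients, data or procedures. The downside is that the study gives up a claim about standard therapy that it cannot support.

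### Patients choose their own group by accepting or declining HBOT, and the only between-group test named is an independent t-test on an unstated quantity, so the comparison cannot by itself support a causal claim

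*Protocol*

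**What the plan says.** The Methods describe a controlled before-and-after study ("This study uses pretest and posttest control group design"). Its purpose is "to know the role of standard therapy and combination therapy (standard therapy with adjuvant HBOT) to decrease HbA1c levels, leukocyte count, and serum creatinine levels".

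Groups are formed by the patient's decision. On one side: "If they are willing to participate in the study and use HBOT was grouped to combination therapy". On the other: "if they are willing to participate in the study but do not want to use HBOT was grouped to standard therapy". The protocol mentions no randomisation, matching or stratification, and claims none.

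Baseline values exist for every patient: "All patients were taken blood test for HbA1c levels, leukocyte count, and serum creatinine levels before debridement". The same tests are repeated after two weeks. Thirty patients are included; group sizes are not given.

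The statistical paragraph names two tests: "Analysis pretest and posttest values on both groups were used paired T-test and independent T-test". The significance level is 0.05.

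**The concern.** The control group consists of people who refused the treatment under study. Willingness to attend ten 90-minute chamber sessions in two weeks could plausibly go with severity, frailty or adherence. The protocol does not show that it does, but nothing in the allocation rule prevents it.

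The paired t-test works within a group, so the question about HBOT rests on the independent t-test. That test has a 5% risk of a false claim about HBOT only if accepters and decliners would have had the same distribution of the compared quantity without HBOT. If they would not, a significant result may reflect who chose HBOT and not what HBOT did. The bias could equally hide a real effect. Because the aim is phrased as an effect, a difference between groups is likely to be read causally.

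**Working it through.** The protocol states no effect size, SD, correlation or power, so there is no figure of its own to reproduce. The check asks how far the named test can drift from 5% under plausible selection.

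**From the protocol:** 30 patients; significance level 0.05; each marker measured before and after.

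**Assumed:** two-sided test; roughly even split; no HBOT effect; SD of 1 before and after; pre-post correlation r; a baseline gap of d SD between the self-chosen groups.

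**Step 1. Closed-form check, choice related to baseline, 15 per group.**
- Standard error of a difference in SD units: √(1/15 + 1/15) = 0.365.
- Test on post-test values: expected difference r × d. With r = 0.7 and d = 0.5 this is 0.35, noncentrality 0.35 / 0.365 = 0.96, rejection rate 0.153.
- Test on changes: standardised difference (1 − r) × d / √(2(1 − r)). With the same inputs, 0.15 / 0.775 = 0.194, noncentrality 0.53, rejection rate 0.081.
- With d = 0 both give 0.05. A 10/20 split gives similar, slightly lower rates (0.141 and 0.077).

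**Step 2. Simulation, 20,000 trials per cell.** It adds the regression of the post-test value on group and baseline. False-positive rates in % are for r = 0.5 / 0.7 / 0.9.

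| Selection | Gap (SD) | t on post-test | t on change | Regression on baseline |
|---|---|---|---|---|
| None | 0 | about 5 | about 5 | about 5 |
| A: choice driven only by the baseline value | 0.47 | 9 / 14 / 20 | 10 / 8 / 6 | 5 / 5 / 5 |
| A | 0.83 | 20 / 36 / 55 | 20 / 14 / 8 | 5 / 5 / 5 |
| B: groups differ by the same amount before and after | 0.47 | 23 / 24 / 24 | 5 / 5 / 5 | 11 / 8 / 6 |
| B | 0.83 | 59 / 59 / 59 | 5 / 5 / 5 | 21 / 14 / 7 |

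The t-test on post-test values fails in both A and B. The t-test on changes fails in A and holds in B; the regression does the reverse.

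**Step 3. How far the two alternatives can differ.** The regression estimate minus the change estimate equals (1 − b) × baseline gap, where b is the within-group slope. With b near r:
- at a 0.47 SD gap: 0.5 × 0.47 = 0.23, 0.3 × 0.47 = 0.14, 0.1 × 0.47 = 0.05 SD;
- at a 0.83 SD gap: 0.42, 0.25 and 0.08 SD.

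**Step 4. An unmeasured factor** with a 0.5 SD effect on the post-test value that also influences choice (r = 0.5 to 0.7):
- Acting on choice in the same direction as baseline: regression 10 to 34%, change 5 to 30%.
- Acting in the opposite direction: regression 10 to 34%, change 10 to 56%, and the post-test t-test 5 to 20% because biases partly cancel.

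No analysis is safe in general. The regression fails here even where choice also depends on the measured baseline, so its validity requires that choice depends only on that baseline.

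**The case against.** The strongest reply has four parts.

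*The design is open about itself.* This is right. A reader might infer that the protocol presents a preference-based study as a randomised one, or contradicts itself. It does neither. Disclosure does not remove the bias, however, and the aim is still worded as an effect.

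*Adjustment belongs in a statistical analysis plan.* This also stands in part. The absence of a covariate model from the protocol is not in itself an error, and a plan that is not shown may supply one. But the protocol itself fixes the allocation and names the between-group test, so the point does not depend on what such a plan contains.

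*The t-test may be on changes.* It may. A reader might infer that the plan compares post-test values and ignores baseline; the sentence does not commit to that. If the test is on changes, it already uses baseline and is one of the two analyses recommended here. Within A and B, the 55 to 59% rates then do not apply: the change score gives 6 to 20% in A and 5% in B. It remains biased in A, and in most settings with an unmeasured factor.

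*The sizes are hypothetical.* They are. The document gives no SD, correlation, group size or strength of selection, so bias is shown to be possible, not present.

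**Conclusion.** The point holds as a weakness of design and inference that should be fixed. Allocation by acceptance or refusal of HBOT, followed by an independent t-test on an unstated quantity, leaves the between-group comparison open to self-selection bias of unknown size and direction. A significant result cannot by itself be read as an effect of HBOT.

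The simulated rates show sensitivity under assumed SDs, correlations and selection strengths; they do not estimate this trial's error rate. A reader might take the table to show that the result is wrong, or that baseline adjustment would cure the problem. The document supports neither: it gives no evidence on how accepters and decliners differ, and no analysis of these data removes bias from unmeasured reasons for the choice.

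**What to change.** 1. Describe the study as a non-randomised, preference-based comparison, and word any between-group conclusion as an association.
2. State which quantity the independent t-test compares, and do not rest the conclusion on an unadjusted comparison of post-test values. For each marker report, with 95% confidence intervals, both the regression of the post-test value on group and baseline value and the between-group difference in change. Report both, whichever is more favourable, and treat the result as inconclusive if they disagree.
3. State the conditions. The regression is unbiased only if choice depends only on the measured baseline value and the model is correct. The change score is unbiased only if the groups would differ by a stable amount without treatment. Neither removes bias from unmeasured factors.
4. The Methods are written in the past tense, so data may already exist. If data have been collected or seen, label the added analyses post hoc. If an analysis plan already specifies them, align the protocol sentence with it.

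The cost is small. No new patients or measurements are needed, and the regression uses one more residual degree of freedom (28 to 27). Its simulated 95% confidence half-width at correlation 0.5 is 0.67 SD, against 0.76 for either t-test, without selection, and 0.73 against 0.74 at a 0.83 SD gap. At correlation 0.9 and that gap it is slightly wider than the change score (0.37 against 0.34 SD). The real price is a more modest claim that may prove inconclusive.

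### The only pretest precedes debridement, so a significant paired fall in the combination group measures surgery plus all later therapy and cannot be read as an HBOT effect

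*Protocol*

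**What the plan says.** All of the relevant text is in the Protocol's Methods.

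- **Pretest.** "All patients were taken blood test for HbA1c levels, leukocyte count, and serum creatinine levels before debridement, then grouped for standard therapy", the alternative group receiving the same therapy plus 10 HBOT sessions.
- **Posttest.** "At the end of therapy, all blood tests were performed again in both groups". No other draw is described.
- **Surgery.** To be eligible, patients must have "underwent debridement with or without toe amputation". Surgery is therefore common to both groups, but its extent varies between patients.
- **Duration.** Of the HBOT course: "This therapy is given five sessions in a week, so it takes two weeks".
- **Grouping.** Patients choose: "if they are willing to participate in the study but do not want to use HBOT was grouped to standard therapy". The total is 30 patients; the split between groups is not stated.
- **Aim.** "to know the role of standard therapy and combination therapy (standard therapy with adjuvant HBOT) to decrease HbA1c levels, leukocyte count, and serum creatinine levels".
- **Analysis.** Paired and independent t-tests on pretest and posttest values, with significance at p < 0.05.

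Standard therapy is not defined. The intervals between pretest, operation, first session and posttest are not given. That the operation precedes the first HBOT session is the natural reading, but it is not stated outright.

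**The concern.** An operation on an advanced foot ulcer falls inside every patient's pretest-to-posttest interval. It is reasonable to expect that removing infected tissue lowers the leukocyte count, and creatinine too where infection had raised it, whether or not HBOT follows. That is a clinical inference, and the Protocol gives no figure for it.

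Two consequences follow, of unequal weight.

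1. **Paired test.** In the combination group, the paired t-test asks whether surgery, standard therapy and HBOT together moved the marker. A small p-value says nothing specific about HBOT. The title presents HBOT as improving these markers, so there is a real risk that a significant paired fall is offered as evidence for it.
2. **Between-group test.** Here a shared surgical effect drops out. Because patients choose their group, surgical extent may differ between the groups, and that difference would pass into the contrast. Adjusting for the pretest alone does not remove it, because the operation comes after the pretest.

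**Working it through.** The Protocol states no mean, SD, effect size or power, so there is no figure of its own to reproduce. Only the session count can be checked: 10 sessions / 5 per week = 2 weeks, which agrees.

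**What each test estimates.** Let S be the effect of surgery plus standard therapy on the change and H the effect of HBOT.

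- Paired test, standard group: S
- Paired test, combination group: S + H
- Difference in changes, equal surgical effect: (S + H) - S = H
- Difference in changes, extra surgical effect D in the combination group: H + D

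So the paired test can reject when H = 0, while the between-group test is disturbed only if D is not zero.

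**Paired test with H = 0.** Assumptions: 15 patients in the group, SD of change 5 x10^9/L, surgical fall f, two-sided 5% test. The non-centrality is (f / 5) x sqrt(15), referred to a t distribution with 14 degrees of freedom (critical value 2.145).

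| Surgical fall f | Non-centrality | Significant trials |
|---|---|---|
| 3 | 0.6 x 3.873 = 2.32 | 58% |
| 4 | 0.8 x 3.873 = 3.10 | 82% |
| 5 | 1.0 x 3.873 = 3.87 | 95% |
| 6 | 1.2 x 3.873 = 4.65 | 99% |

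The result depends on the unstated split: with 10 patients in the group, a fall of 3 gives 40% instead of 58%.

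In SD units, by simulation (40,000 runs, H = 0):

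| Surgical shift (SD of change) | 15 in group | 10 in group |
|---|---|---|
| 0 | 5% | 5% |
| 0.25 | 15% | 11% |
| 0.5 | 44% | 30% |
| 0.75 | 77% | 56% |
| 1.0 | 95% | 80% |

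With 15 per group, the standard group's paired test gives the same rates.

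**Between-group test with H = 0.**

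- Equal surgical effect (D = 0): about 5% rejections at every surgical shift, with 15/15 and with 10/20.
- Unequal surgery: suppose toe amputation adds a further fall of 2 to 4 x10^9/L and is done in 60% of one group and 30% of the other. Then D = (0.60 - 0.30) x 2 = 0.6, up to (0.60 - 0.30) x 4 = 1.2. With SD 5 and 15 per group, the non-centrality is (D / 5) / sqrt(2/15): 0.12 / 0.365 = 0.33 and 0.24 / 0.365 = 0.66. On 28 degrees of freedom the rejection rates are 6.2% and 9.7%.
- A larger D, in SD units: 0.25 gives about 10% and 0.5 about 26% (15/15); about 9% and 24% (10 HBOT, 20 standard).

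**The case against.** The strongest reply is that the design has a control group. All patients are bled at the same point before surgery, all are debrided, and all are bled again at the end. A surgical effect common to both groups cancels, and the Protocol plans an independent t-test as well as the paired ones. Nowhere does it say that a paired fall will be taken as the HBOT effect. This stands, and it confines the large figures to the paired tests.

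Second, the aim covers the role of standard therapy itself. If debridement is part of that therapy, a pre-debridement value is the proper starting point, and a later baseline would discard part of what is being studied. This also stands, subject to standard therapy being undefined.

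Third, any imbalance in surgical extent comes from patient choice, not from when the blood is drawn. That is correct. The timing matters here only because it leaves the imbalance inside the measured change.

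A reader might infer two stronger claims, and the text supports neither.

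- *That the pretest is not a pre-HBOT value.* It does precede HBOT. What is missing is a value after surgery and just before the first session.
- *That the baseline must be moved to after surgery.* Early post-operative leukocytes carry a stress response that may itself vary with surgical extent, so the imbalance could re-enter through the new baseline. The paired test would not be rescued either, since standard therapy continues and a resolving stress response is itself a fall. Nor does the Protocol say that post-operative bloods are routinely taken.

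**Conclusion.** The point holds for the within-group tests. With one draw before surgery and one at the end of therapy, a significant paired fall in the combination group cannot be attributed to HBOT. Under the assumed surgical falls, the test would be significant in 58% to 99% of trials with no HBOT effect (15 in the group); smaller shifts or a smaller group lower this, but it stays above 5% for any non-zero shift.

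For the between-group comparison, the timing alone causes no bias. Unequal surgical extent would add a bias of unknown size; under the illustrated imbalance it is modest, about 6% to 10% false positives against a nominal 5%.

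The surgical falls, the SD of 5, the amputation rates, the group sizes and the two-sided test are all assumptions. The conclusion about what the paired test estimates needs none of them. It needs only that debridement falls between the two draws, which is the natural reading of the schedule.

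**What to change.** 1. State in the analysis text that paired changes are reported only as the total change with surgery plus therapy, and are not evidence for HBOT.
2. Base any HBOT conclusion on the between-group comparison of posttest values, in a linear model with group, pretest value and toe amputation (yes/no). Take amputation as recorded at the operation before the first session, so that the covariate cannot be affected by HBOT. Tabulate toe amputation by group.
3. Where a blood count and creatinine after surgery and before HBOT already exist at a comparable time in both groups, repeat the comparison with them as baseline, as a sensitivity analysis only.
4. Say whether debridement counts as standard therapy, and state the order and intervals of pretest, operation, first session and posttest.

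**Cost.** A few sentences and one recorded variable. Two covariates take the residual degrees of freedom from 30 - 2 = 28 to 30 - 4 = 26. No extra draw is required. The sensitivity baseline carries the post-operative stress response and may be missing for some patients. Adjusting for toe amputation addresses that one difference; it does not make groups formed by preference comparable in other respects.

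### Grouping comes after the pretest and the patient's choice of HBOT is undated, so allocation can depend on the baseline outcome values, and the stated t-tests do not adjust for them

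*Protocol*

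**What the plan says.** All of this is in the Methods section of the protocol.

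- **Allocation paragraph.** There is no randomisation. "All patients were briefed on the study research using HBOT", and the group follows from the answer: "If they are willing to participate in the study and use HBOT was grouped to combination therapy", while those who agree to take part but "do not want to use HBOT was grouped to standard therapy". Consent is signed after the explanation. The paragraph does not place the choice before or after any blood test.
- **Procedure paragraph.** All patients have blood taken for HbA1c, leukocyte count and "serum creatinine levels before debridement, then grouped for standard therapy or standard therapy with 10 sessions of HBOT"; the sentence thus puts grouping after the pretest. The three pretest variables are also the three outcomes, measured again at the end of therapy.
- **Criteria paragraph.** Having undergone debridement, with or without toe amputation, is an inclusion criterion. Taken literally, eligibility is complete only after the pretest.
- **Statistical paragraph.** "Analysis pretest and posttest values on both groups were used paired T-test and independent T-test". It states no adjustment for baseline and does not say whether the independent test compares changes or posttest values.

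**The concern.** Measuring the baseline before allocation is harmless when allocation cannot respond to what was measured. Here allocation is an open choice, and nothing says that it was fixed before the results existed or that the results were withheld until then. The group could therefore depend on the measured pretest, including its random error.

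This can be separated from self-selection in general. Willingness recorded before the draw may reflect how ill the patient is, but it cannot reflect the chance error of a sample not yet taken.

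If patients with high values tend to choose HBOT, their group falls further on retesting without any treatment effect. The paired test within that group and a comparison of changes would both show this as benefit. A comparison of posttest values would instead carry the higher starting level forward and count against HBOT. Selection in the other direction reverses both signs.

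**Working it through.** The protocol gives no effect size, power or variance, so there is no figure of its own to reproduce. The check asks how large the bias could be if the choice depends on the pretest.

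**Inputs from the protocol:** 30 patients in total; paired and independent t-tests; 0.05 level.

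**Assumptions:** two-sided tests; pretest and posttest bivariate normal with SD 1; no HBOT effect; pre-post correlation ρ; the strength of selection.

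**Formulas.** Let G be the pretest difference, HBOT minus standard therapy, in SD. When the choice depends only on the measured pretest and chance:
- expected difference in change = −(1 − ρ) × G
- expected difference at posttest = ρ × G

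**Model A.** Patients above the median pretest value enter HBOT with probability p, the rest with 1 − p. The mean of a standard normal variable above its median is √(2/π) = 0.798, so G = 2 × (2p − 1) × 0.798.
- p = 0.6: G = 2 × 0.2 × 0.798 = 0.32
- p = 0.7: G = 2 × 0.4 × 0.798 = 0.64

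The differences below come from the formulas, the false-positive rates from 6,000 simulated trials per setting. The Monte Carlo standard error is √(q(1 − q)/6000) for a rate q, about 0.3 to 0.5 percentage points.

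| p | ρ | Difference in change (SD) | Difference at posttest (SD) | False positives, change | False positives, posttest |
|---|---|---|---|---|---|
| 0.5 | 0.3–0.7 | 0 | 0 | about 5% | about 5% |
| 0.6 | 0.3 | −0.22 | +0.10 | 8.9% | 5.4% |
| 0.6 | 0.5 | −0.16 | +0.16 | 7.4% | 7.5% |
| 0.6 | 0.7 | −0.10 | +0.22 | 6.2% | 9.3% |
| 0.7 | 0.3 | −0.45 | +0.19 | 17.0% | 8.2% |
| 0.7 | 0.5 | −0.32 | +0.32 | 13.3% | 13.7% |
| 0.7 | 0.7 | −0.19 | +0.45 | 10.2% | 22.8% |

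The simulated differences in change (−0.23, −0.16, −0.10 and −0.44, −0.32, −0.19) agree with the formula.

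**Model B.** Groups of 15 and 15 (assumed, since the split is not stated), with the choice correlated 0, 0.3, 0.5 or 0.8 with the pretest, ρ from 0.5 to 0.9, and 20,000 trials per setting.
- Correlation 0: every test stays at 4.8% to 5.3%.
- Correlation 0.3 (G about 0.47): false positives on change are 9.5% at ρ = 0.5, 7.7% at 0.7 and 6.0% at 0.9; on posttest values 9.7%, 13.5% and 20.6%.
- Correlation 0.8 (G about 1.24): on change 40.9%, 26.3% and 11.4%; on posttest values 40.8%, 73.5% and 95.5%.
- Paired test within HBOT, over the three non-zero correlations: 5.4% to 22.8%.
- Posttest compared with the pretest as covariate: 4.8% to 5.2% in every setting, with bias about 0.

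**What recording the choice early does not remove.** Suppose the choice follows visible severity that correlates 0.7 (assumed) with the pretest, with selection as at p = 0.7. The pretest gap is then about 0.7 × 0.64 = 0.45 SD (0.44 in simulation), even though no blood result was known.

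**The case against.** The case on the other side is substantial, and most of it stands.

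- **The order is normal.** A pretest-posttest design needs a pretest before treatment, and the calculations show no bias from the order alone. This stands: the bias is conditional on the choice depending on the pretest values.
- **The mechanism is not in the text.** A reader might infer that clinicians saw poor results and steered those patients to HBOT, so that the comparison is tilted in its favour by construction. The documents do not support that. They mention a briefing and the patient's own willingness, with no advice based on results. The direction of any dependence is unknown, and the quantity used in the independent test is not stated, so the net direction of bias is undetermined.
- **The choice may already come first.** The allocation paragraph can be read as fixing the choice at consent, with the later grouping meaning only that treatment started. That reading is fair. The inclusion criterion on debridement allows the later reading equally well. The timing is unclear; it is not shown to be contradictory.
- **The root problem is self-selection.** True, and it is the larger one. What this point adds is narrower: dependence on the measured pretest and its error, which can be closed while self-selection stays.
- **The sizes are illustrative.** They rest on assumed selection and correlation. With mild selection or high correlation, the excess error on change is small.

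**Conclusion.** The point holds as a gap in timing that should be closed. It is not evidence that a bias occurred. The protocol lets the HBOT choice be made after the baseline values of the three outcomes are known, and the t-tests it names would not correct for a choice that depends on them.

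Under no HBOT effect, mild to moderate selection (0.6 against 0.4, or 0.7 against 0.3) and correlations of 0.3 to 0.7, false positives run from 6% to 17% on change and from 5% to 23% on posttest values. The two biases have opposite signs. If the choice is unrelated to the pretest, the rate stays near 5%.

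These figures rest on assumed selection strength, correlation and normality, and would differ between HbA1c, leukocytes and creatinine. The result for the covariate-adjusted comparison holds when the choice depends only on that outcome's measured pretest and chance. It does not extend to unmeasured reasons for choosing HBOT.

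**What to change.** **If patients are still being enrolled.** Reconcile the allocation and procedure paragraphs:
- Enter the patient's choice (HBOT or no HBOT) on the dated consent form before the pretest blood is drawn, and reword the procedure sentence to match.
- Confirm the debridement criterion afterwards, because it cannot be met at that moment.
- Form the analysis groups from the recorded choice and report any later change of choice.
- Compare posttest values between groups with the pretest value of the same outcome as covariate, in place of an unadjusted independent t-test.

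**If enrolment is complete.** The past tense of the protocol may suggest this ("Thirty diabetic patients with DFU Wagner 3-4 were participated in this study"). The consent entry can then no longer be added. Report when each choice was made relative to the pretest results, as far as records allow, and use the baseline-adjusted comparison.

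**In both cases**, state self-selection by willingness and by visible severity as a limit, since neither step removes it.

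**Cost.** One dated line on the consent form, one reworded sentence and one covariate in the model. The small downside is that a patient who changes their mind after the pretest is analysed in the group first recorded.
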